6.6.1.4. Consumption

The total annualized rFVIII Fc consumption (IU/kg) will be calculated for each patient using the following formula:

$$\text{Annualized consumption} = \frac{\text{Total IU/kg of rFVIII Fc during the efficacy period}}{\text{Total number of days during the efficacy period}} \times 365.25$$

The total amount of rFVIII Fc received will be the sum of the nominal IU/kg administered for each injection based on the units of rFVIII Fc as recorded from the patient's EPD and eCRF and his most recent weight.

Total annualized rFVIII Fc consumption per patient will be determined for the efficacy period (i.e., excluding the PK assessments and surgery/rehabilitation periods [major surgeries]). Total annualized consumption per patient will also be derived based on treatment regimen and overall.

Consumption is a secondary endpoint in this study. A description of how consumption will be summarized is described in Section 7.4.7.

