## **10.5. Non-Medical Treatment With rFVIII Fc**

During the study, subjects' parents/caregivers may attend training sessions on administration of rFVIII Fc. Administration of rFVIII Fc to subjects for training purposes will be considered non-medical treatment. Such training is permitted and must be recorded in the EPD. However, administration of the first dose of rFVIII Fc must be performed under supervision in the clinic. Data from this time period will be excluded from the analysis of consumption.

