5.2.1. Start Date and Time of the First Treatment Regimen

The start date and time of the first treatment regimen is defined as either:

- The date and time of the first rFVIII Fc dose for patients beginning on a prophylactic treatment regimen, as per the treatment assignment eCRF data
- The date and time 120 hours after the date and time of the baseline PK dose, for patients beginning on an episodic treatment regimen, as per the treatment assignment eCRF data

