5.2.2. End Date and Time of the Last Treatment Regimen

The end of the last treatment regimen will be either:

- The date and time of the last rFVIII Fc dose for patients whose last treatment regimen was prophylaxis, ITI, or if they ended the study in a surgical/rehabilitation period
- At 23:59 on the day of the last non-safety follow-up study visit for patients whose last treatment regimen was episodic.

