5.4.2.1. Adjustments Due to Surgical/Rehabilitation Periods

For analysis purposes, the efficacy period for a given treatment regimen will be adjusted for all surgical/rehabilitation periods (major and minor). The start and end of the efficacy period for a given treatment regimen are adjusted as follows:

- For patients on a prophylactic regimen before the start of a surgical/rehabilitation period, the efficacy period for the prophylactic regimen continues up to the last dose (for prophylaxis or bleeding) before the start of the surgical/rehabilitation period.
- For patients on the episodic regimen before the start of a surgical/rehabilitation period, the efficacy period for the episodic regimen continues up to 1 minute before the start of a surgical/rehabilitation period.
- For patients on a prophylactic regimen following the end of a surgical/rehabilitation period, the efficacy period for the prophylactic regimen starts or re-starts (depending on whether there is a treatment regimen change during the surgical/rehabilitation period) at the first prophylactic dose following the end of the surgical/rehabilitation period.
- For patients on the episodic regimen following the end of a surgical/rehabilitation period, the efficacy period for the episodic regimen starts or re-starts (depending on whether there is a treatment regimen change during the surgical/rehabilitation period) at 00:01 on the day following the end of the surgical/ rehabilitation period.

Start and end dates/times for the efficacy period for given treatment regimens and treatment regimen changes will be adjusted for each surgery (major or minor) as necessary.

For patients on a prophylactic regimen before the start of a surgical/rehabilitation period, the interval of time between the last dose before a surgical/rehabilitation period and the start of the surgical/rehabilitation period will not be attributed to the efficacy period for the prophylactic regimen. By definition, there should not be any treated bleeding episodes in this interval of time.

For patients on a prophylactic regimen following the end of a surgical/rehabilitation period, bleeding episodes that occur after discharge from a rehabilitation facility but before the next prophylactic dose will be attributed to the surgical/rehabilitation period and hence not counted towards the annualized bleeding rate (ABR).

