6.6.1.3. Prophylactic Dose (IU/kg) and Dosing Interval (days)

The prescribed prophylactic dose and dosing frequency will be summarized categorically for the prophylactic and ITI treatment periods.

Because dosing in this study is based on variable doses and dosing intervals, average weekly dose (daily for the ITI treatment regimen) and average dosing interval will be derived for each patient to characterize the amount of rFVIIIIFc received for prophylaxis. Descriptive statistics will be provided using the FAS.

The average weekly (daily for ITI) prophylactic dose (IU/kg) and the average prophylactic dosing interval will be based on prophylactic doses that are not separated by a bleeding episode or major surgical/rehabilitation period. Data to be included in the calculations, specifically the prophylactic doses and the total duration of prophylactic treatment, will come strictly from intervals representing two consecutive prophylactic doses (PR) during the efficacy period (see Section 5.4.2 for a description of the efficacy period). The sum of doses at PR_x and the sum of interval durations (PR_{x+1} minus PR_x) will be determined across all evaluable intervals of PR_x to PR_{x+1}. As such, when an event (a bleeding episode or surgery) is encountered, the interval stops at the prophylactic dose prior to the event and continues with the first prophylactic dose after the event. The last PR dose in the study will be the end of the last interval used for these calculations.

$$\text{Average weekly prophylactic dose} = \frac{\text{Sum of doses at PR}_x \times 7}{\text{Sum of days in PR intervals}}$$

$$\text{Average daily prophylactic dose} = \frac{\text{Sum of doses at PRx}}{\text{Sum of days in PR intervals}}$$

$$\text{Average prophylactic dosing interval} = \frac{\text{Sum of days in PR intervals}}{\text{Number of PR intervals}}$$

Prophylactic dosing will be further characterized by the number of prescribed changes in the dose and the number of prescribed changes in the dosing interval. Dose and dosing interval changes are based on recommendations made by the Investigator and may or may not reflect whatever modifications a patient actually made to his dosing regimen. The number of prescribed changes in the dose level and the number of prescribed changes in the dosing schedule will be summarized categorically (0, 1, 2, 3, 4, >4) and with descriptive statistics.

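### Annualized consumption (SAP 6.6.1.4) can count one dose too many in each prophylaxis segment that opens and closes on a counted dose, and its surgery and training-dose exclusions do not match SAP 5.4.2.1 and protocol 10.5

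*SAP*

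**What the plan says.** SAP 6.6.1.4 defines annualized consumption as total IU/kg in the efficacy period, divided by the days in that period, times 365.25. For the numerator it states: "The total amount of rFVIII Fc received will be the sum of the nominal IU/kg administered for each injection". It describes the period as "excluding the PK assessments and surgery/rehabilitation periods [major surgeries". It has no rule for a dose given exactly at a period boundary.

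The day-count is built elsewhere in the SAP:

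- **Start (5.2.1):** "The date and time of the first rFVIII Fc dose for patients beginning on a prophylactic treatment regimen". A patient who moves from episodic treatment starts prophylaxis at the first prophylactic dose (5.2.3).
- **End (5.2.2):** "The date and time of the last rFVIII Fc dose for patients whose last treatment regimen was prophylaxis, ITI". For episodic treatment it is instead: "At 23:59 on the day of the last non-safety follow-up study visit for patients whose last treatment regimen was episodic".
- **Surgery (5.4.2.1):** "the efficacy period for a given treatment regimen will be adjusted for all surgical/rehabilitation periods (major and minor". Prophylaxis time stops at the last dose before the surgical period and restarts at the first prophylactic dose after it.
- **Gaps over 28 days (5.4.2.2):** prophylaxis time stops at the injection that opens the gap and restarts at the injection that closes it.
- **PK doses:** 6.6 takes them out of consumption, and 5.4.5 defines no PK period.

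For the average weekly dose, 6.6.1.3 sums only the doses that open an interval: "The last PR dose in the study will be the end of the last interval used for these calculations". On doses given to train caregivers, protocol 10.5 says: "Data from this time period will be excluded from the analysis of consumption".

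**The concern.** A segment that runs from one dose to another contains one more dose than it has dosing intervals. If every dose is summed, the closing dose enters the numerator although none of the days it covers are counted. This recurs in each segment, so a surgery or a long gap adds to it. The distortion is upward, and it is largest for short courses of prophylaxis.

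The exclusions raise a separate problem. Sections 6.6.1.4 and 5.4.2.1 disagree on minor surgery, and the protocol's training-dose exclusion has no counterpart in 6.6.1.4. Two programmers could therefore derive different values from the same text.

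Consumption is both a secondary objective and a secondary endpoint, and the derivation serves the interim and final analyses.

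**Working it through.** The documents give no expected consumption figure, so there is nothing to reproduce. The check applies the 6.6.1.4 formula to a regular course.

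**Inputs.** n prophylactic doses of size D at a constant interval t, in k segments that each open and close on a counted dose, with no bleed treatment. The base case n = 50 comes from the planned minimum of 50 exposure days, taking each as one prophylactic dose. The SAP accepts 2 prophylactic injections as the minimum for an evaluable period (5.4.2). The adjustment range of 25 to 65 IU/kg at 3- to 5-day intervals (3.1.5.2) is used for illustration only.

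**Formula.** Days = (n − k)t. Counting every dose gives nD/[(n − k)t] × 365.25. The dosing rate is (D/t) × 365.25. The ratio of the two is n/(n − k). Leaving out each closing dose, as 6.6.1.3 does, gives a ratio of 1.

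| n | k | n − k | Overstatement |
|---|---|---|---|
| 100 | 1 | 99 | +1.0% |
| 50 | 1 | 49 | +2.0% |
| 50 | 2 | 48 | +4.2% |
| 50 | 3 | 47 | +6.4% |
| 20 | 1 | 19 | +5.3% |
| 10 | 1 | 9 | +11.1% |
| 2 | 1 | 1 | +100% |

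In annual units, for 50 doses in one segment:

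- 25 IU/kg every 5 days: 1,864 instead of 1,826 IU/kg per year.
- 65 IU/kg every 3 days: 8,075 instead of 7,914 IU/kg per year.

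**Segments that escape.**

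- Episodic time ends at 23:59 on a visit day, or 1 minute before the first prophylactic or ITI dose or the surgical period.
- A switch from prophylaxis to ITI with no prophylactic dose that day ends prophylaxis at 23:59 the day before.
- Prophylaxis after ITI opens at 00:01, or 1 minute after an ITI dose, so it does not open on a counted prophylactic dose.

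**PK offset.** Take a prophylaxis starter whose first of 50 doses is the baseline PK dose, followed by a normal interval. The PK dose leaves the numerator but its days stay. One segment gives 49/49 = 1.000. With one surgery (two segments) the ratio is 49/48, or +2.1%. A patient coming from episodic treatment has no such offset.

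**Minor surgery.** Section 5.4.2.1 takes major and minor surgical periods out of the efficacy period, and 5.4.3 defines both in the same manner. Section 6.6.1.4 describes the same period as excluding major surgeries only. If 5.4.2.1 governs, the bracketed words in 6.6.1.4 are wrong. If 6.6.1.4 governs, consumption and bleeding rate use different day-counts, although 7.1 bases both on the efficacy period.

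**Training doses.** Protocol 10.5 excludes them; 6.6.1.4 does not, and SAP Section 10 lists no such change. Their days stay in the denominator either way. Assuming 1, 2, 5 or 10 training doses on top of 50 regular doses of equal size, consumption rises by 2%, 4%, 10% or 20% relative to the protocol definition.

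**The case against.** The strongest reply is that the endpoint as a whole is not shown to be overstated. Several parts of this stand.

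- **Cancellation.** For some prophylaxis starters the PK offset removes the effect entirely. The baseline visit may also follow up to three doses (SAP 5.1.2.2). A PK dose that came second or third and took up a normal interval would offset the closing dose in the same way.
- **Minor surgery.** A reader might infer that minor-surgery doses are counted while their days are dropped. With 50 prophylactic doses in two segments and an assumed 1, 3 or 5 surgical doses of regular size, that would give 51/48, 53/48 or 55/48: +6.3%, +10.4% or +14.6%, closing doses included. The SAP does not specify this. It uses one period for numerator and denominator, and applying either section's rule to both leaves no such mismatch.
- **Short periods.** A reader might take the pre-inhibitor period as the worst case. It ends at the date of the first positive sample (5.4.7), not at a dose. The +100% figure belongs only to the two-injection minimum.
- **Comparison with 6.6.1.3.** The weekly dose uses only prophylactic intervals free of bleeds and surgery, whereas consumption includes bleed treatment. The two would differ in any case, so 6.6.1.3 is a model for handling the closing dose and not proof of error.
- **A blanket correction.** Dropping the last dose of every segment would give a single-segment starter with a PK first dose 48/49, about −2%. It could also delete a bleed-treatment dose, because 5.4.2.1 lets a segment before surgery close on one.

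What remains is that 6.6.1.4 has no boundary-dose rule, conflicts with 5.4.2.1, and omits the protocol's training exclusion without saying so.

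**Conclusion.** The point holds in limited form. On the natural reading, in which every injection in the period is summed, consumption is overstated by n/(n − k) for prophylaxis segments that open and close on a counted dose. That is about 2% per segment at 50 doses and 11% at 10 doses in one segment. These figures assume equal doses and intervals; the number of segments per patient is an illustration. Because the offset depends on how a patient entered prophylaxis, the error is not uniform across patients.

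The surgery conflict and the missing training exclusion are inconsistencies to reconcile. The documents do not establish a size for either, and the training issue is an undeclared departure from the protocol rather than a day-count mismatch. All analyses are descriptive, so no test or primary result is affected.

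**What to change.** Amend SAP 6.6.1.4 as follows:

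1. **Boundary dose.** Leave the closing dose of a segment out of the numerator when it is a prophylactic dose and the segment opened on a counted dose. Keep all bleed-treatment doses. For prophylaxis starters whose first dose is the PK dose, either start the consumption day-count at the first non-PK dose (48 doses over 48 intervals in the example above) or make no closing-dose deduction in that first segment (49 over 49). State also how the interval after a PK dose given second or third is handled.
2. **Surgery.** Change the bracketed restriction so that it names major and minor surgeries; doses and days then both follow 5.4.2.1.
3. **Training doses.** Exclude doses recorded as non-medical or training, as protocol 10.5 states, or list the change in SAP Section 10. The diary already captures whether the reason for a dose was medical (protocol 10.2.4.1.4).

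The cost is SAP wording and derivation code. No new data collection is needed.

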The ITI regimen will approximate the high-dose treatment arm of the International ITI Study protocol [Hay and DiMichele 2012] and will utilize single injections of rFVIII Fc 200 IU/kg, daily, consistent with current ITI guidelines [Valentino 2015]. This dosing regimen is also supported by the results of a prospective clinical trial (the International ITI Study) that compared subjects treated with FVIII for ITI at a high dose (200 IU/kg/day) and a low dose (50 IU/kg/3 times per week). Results from this study [Hay and DiMichele 2012] demonstrated that the times to achieve negative inhibitor titer, normal FVIII recovery, and FVIII tolerance were shorter in subjects treated with the high dose of FVIII, compared to subjects treated with the low dose. Furthermore, subjects treated with the high dose for ITI had a lower rate of intercurrent bleeding and fewer hospitalizations due to bleeding than subjects treated with the low dose. Since clearance is expected to be very rapid in the presence of inhibitors, irrespective of the type of FVIII product, the high dose of 200 IU/kg/day evaluated in the International ITI Study will be used in the present study to maximize the potential for rapid tolerization while minimizing bleeding-related adverse events.

If a subject requires surgery while participating in this study, the subject may be treated with the dose and regimen of rFVIII Fc deemed appropriate by the Investigator for the type of surgery. All major surgeries will be reported as serious adverse events (SAEs).

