2.2.2. Secondary Endpoints

The secondary endpoints of the study are as follows:

- The annualized number of bleeding episodes per patient (annualized bleeding rate [ABR])
- The annualized number of spontaneous joint bleeding episodes per patient.
- Assessments of response to treatment with rFVIII Fc for bleeding episodes, using the 4-point bleeding response scale.
- The total number of EDs per patient per year
- Total annualized rFVIII Fc consumption per patient for the prevention and treatment of bleeding episodes.
- The number of injections and dose per injection of rFVIII Fc required to resolve a bleeding episode.
- rFVIII Fc incremental recovery (IR).
- Response to ITI with rFVIII Fc (complete success, partial success, failure, early withdrawal).

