5.1.1.2. Inhibitor Subgroups

Selected tables will further be presented by the following groups:

- Patients in the inhibitor subgroup (see Section 5.1.2.5)
- Patients not in the inhibitor subgroup

For longitudinal data, the safety or efficacy periods included for these groups is the entire period, again as described in Section 5.4.

Patients in the inhibitor subgroup will be further split by the sub-classification of inhibitor as described in Section 5.1.2.5, namely:

- Patients with high-titer inhibitors
- Patients with low-titer inhibitors that meet the clinically meaningful criteria as defined in Section 5.1.2.5
- Patients with low-titer inhibitors that do not meet the clinically meaningful criteria

For this presentation, the analysis of longitudinal data will be presented for the entire safety or efficacy periods, dichotomized as described in Section 5.4.7, i.e.:

- From start of the relevant period up to the date of the positive inhibitor (all patients in the inhibitor subgroup combined)
- From date of positive inhibitor to the end of the relevant period

The definition of a positive inhibitor and the date of onset are described in Section 5.1.2.4.

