5.4.2. Efficacy Period

The efficacy period will be used for the evaluation of efficacy and health outcome endpoints. For a patient to have an evaluable efficacy period over the duration of study, he must have at least 1 day of treatment for an episodic regimen or at least 2 prophylactic injections for prophylactic regimens.

The start and end, and the total duration of the efficacy period for a given treatment regimen is the same as the start and end, and the total duration of that treatment regimen defined in Section 5.2.4 with the exceptions described in the following two subsections. The start of the efficacy period for each patient is the start of their first treatment regimen and the end is the end of their last.

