6.6. Study Drug

Study treatment is described in Section 3.1.2. Study drug administered will be listed by patient for the FAS. This will include the reason for administration (PK assessment, episodic (treatment of a bleeding episode), prophylaxis, ITI, surgery, other) date and time of administration, dose, and dosing intervals, consumption and compliance. It will also include lot number and nominal potency of the lots used.

Except for PK doses, the unit body weight dose (IU/kg) for analysis of dosing will be calculated as the total IU (nominal dose) for each injection divided by the patient's most recent weight in kg prior to the dose of study drug.

PK doses were all 25 IU/kg at the Baseline IR Visit, 50 IU/kg during the ITI regimen for IR and t_{1/2} assessments, and were calculated using the actual potency of the vial (between 80 to 125% of nominal strength) and used partial vials where necessary. Therefore PK doses in the analysis are similarly calculated using the exact number of complete and partial vials, the volume and actual potency of each vial and the patient's most recent weight.

Both types of dose are calculated as follows:

$$\text{Dose (IU/kg)} = \frac{\left(\frac{\text{Total volume administered}}{\text{Volume of vial}} \right) \times \text{Actual/Nominal Potency of Vial}}{\text{Weight (kg)}}$$

PK doses were not used for the purpose of preventing or treating bleeding and therefore the total annualized rFVIII Fc consumption will exclude the IU/kg amount that was used for PK doses. However, data collected over the time in which the PK dose was administered will be included in the safety analyses.

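### Annualized consumption in the inhibitor-subgroup table, and in the per-patient overall value, blends 200 IU/kg/day ITI dosing into an endpoint defined as product used to prevent and treat bleeds

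*SAP*

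**What the plan says.** SAP 2.2.2 defines the endpoint as "Total annualized rFVIII Fc consumption per patient for the prevention and treatment of bleeding episodes". SAP 6.6.1.4 computes it as total IU/kg in the efficacy period, divided by days in that period, times 365.25. The only exclusions it names are PK assessments and major-surgery periods. It then says: "Total annualized consumption per patient will also be derived based on treatment regimen and overall".

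SAP 6.6 gives the reason for the PK exclusion: "PK doses were not used for the purpose of preventing or treating bleeding". Protocol 10.5 likewise keeps training doses out of the consumption analysis. Neither document states a corresponding rule for ITI doses.

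Under SAP 5.4.2 the start of a patient's efficacy period "is the start of their first treatment regimen and the end is the end of their last". For the inhibitor versus no-inhibitor tables, SAP 5.1.1.2 says: "For longitudinal data, the safety or efficacy periods included for these groups is the entire period, again as described in Section 5.4". SAP 7.4.7 plans consumption by regimen and by inhibitor subgroup. SAP Section 12 lists three consumption tables: by regimen, by inhibitor subgroup and by inhibitor sub-classification.

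Protocol 16.2.1 includes inhibitor subjects' efficacy data up to the last negative inhibitor test and has later data summarized separately. Protocol 16.2.3 calls for consumption to be summarized overall as well as for subgroups.

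**The concern.** The plan filters consumption by purpose for PK and training doses but not for ITI, where one day is 200 IU/kg. Under the SAP dosing range of 25 to 65 IU/kg every 3 to 5 days, a day of prophylaxis averages 5.0 to 21.7 IU/kg. Even a short ITI course can therefore dominate a subject's annualized value.

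The inhibitor-subgroup comparison is the most exposed. SAP 5.1.2.5 says high-titer patients must enter ITI or withdraw, so ITI time sits in one column only. The contrast between columns would then largely show who received ITI and for how long, not how much product was needed to prevent and treat bleeds. The value also moves with the ITI days accrued at a data cut: SAP 3.5 runs the same analyses at interim and final, and SAP 7.4.9 allows for ITI still ongoing.

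**Working it through.** **1. Is ITI inside the window?** The minimum criteria in SAP 5.4.2 mention only episodic and prophylactic regimens, which leaves room for doubt. Three other places settle it:
- SAP 5.2.2 names ITI as a possible last regimen, so the efficacy period can end with it.
- SAP 6.6.2.2 assesses compliance with ITI dosing during the efficacy period.
- The adjustments in SAP 5.4.2.1 and 5.4.2.2 remove surgical periods and prophylactic gaps over 28 days, and nothing for ITI.

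**2. Which outputs are affected?**
- By regimen: not affected. ITI has its own group (SAP 5.1.1.1).
- By inhibitor sub-classification: split at the first confirmed positive sample (SAP 5.1.1.2, 5.4.7), so ITI enters only the later part.
- By inhibitor subgroup: affected, because the whole period is pooled.
- Overall: a per-patient value is derived, but the SAP lists no overall table, and SAP 5.1.1 says efficacy presentations generally carry no total column.

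**3. Size for one ITI subject.** The plan states no consumption figure, so there is nothing to reproduce. Inputs are 200 IU/kg/day for up to 33 months (SAP 3.1.2.3), then 3 months of taper and 9 of monitoring (Protocol 7.3.2), and prophylaxis of 25 to 65 IU/kg every 3 to 5 days (SAP 3.1.5.2). Assumption: all non-ITI time runs at the prophylaxis rate r, because the taper doses are redacted. With f the ITI share of days,

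factor = [f × 200 + (1 − f) × r] / r

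| ITI share of period | 25 every 5 days (r = 5.0) | 45 every 4 days (r = 11.25, assumed midpoint) | 65 every 3 days (r = 21.67) |
|---|---|---|---|
| 1 of 12 months | 4.2 | 2.4 | 1.7 |
| 3 of 12 months | 10.8 | 5.2 | 3.1 |
| 12 of 24 months | 20.5 | 9.4 | 5.1 |
| 33 of 45 months | 29.6 | 13.3 | 7.0 |

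The two ends in full:
- Low: (1 × 200 + 11 × 21.67) / 12 = 36.53 IU/kg/day, or 13,342 IU/kg/yr against 7,914. Factor 1.7.
- High: (33 × 200 + 12 × 5) / 45 = 148 IU/kg/day, or 54,057 IU/kg/yr against 1,826. Factor 29.6. Adding 3 months before ITI (33 of 48 months) gives 27.8.

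Protocol 10.2.3 also allows up to 80 IU/kg. At 80 every 3 days the 1-of-12-month factor is 1.5.

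**4. With ITI doses and days both removed,** the subject's value returns to r × 365.25: 1,826 to 7,914 IU/kg/yr across the table's range, and 4,109 at the midpoint. Removing the doses but keeping the days would understate use.

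**5. Group mean.** If a share p of a group receives ITI with factor F, and all share the same r, the mean is multiplied by 1 + p(F − 1). With F = 9.4 and p assumed at 25%, 50% or 75%, this is 3.1, 5.2 or 7.3. The documents do not give p.

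**The case against.** **ITI doses are not like PK doses.** SAP 6.6.1.3 derives the ITI daily average under the label of prophylactic dose, and Protocol 5.3 chose the high dose "to maximize the potential for rapid tolerization while minimizing bleeding-related adverse events". The endpoint is also called total consumption. This stands in part: ITI may prevent some bleeding, and an ITI-inclusive total is a legitimate quantity. But Protocol 7.2.1 expects much lower exposure during ITI because of the inhibitor, and Protocol 10.2.5.2.3 allows bypassing agents for bleeding during ITI. The dose therefore does not measure what bleed prevention requires. ITI is also recorded as its own injection reason (SAP 6.6, 6.6.1.1).

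**The consumption question is answered elsewhere.** This also stands in part. The prophylaxis column of the by-regimen table contains no ITI-regimen doses, and the sub-classification tables show pre-inhibitor consumption free of ITI. What remains is one listed table and one derived value.

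**Nothing is tested.** True: every comparison is descriptive, and SAP Section 4 says the interim and final populations differ anyway. The table can still mislead when read.

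**A reader might infer that the reported figures will be about 9 to 13 times prophylaxis use.** The documents do not support that as a general statement. It fits, for example, 50 IU/kg every 3.5 days (14.29 IU/kg/day) with 60 days of prophylaxis, 90 to 1,004 days of ITI and no time afterwards: (60 × 14.29 + 90 × 200) / 150 = 125.7, a factor of 8.8, rising to 13.3. Complete successes have about a year of taper and monitoring, which SAP 5.2.3 and 3.1.5.3 place on the prophylactic regimen. Adding 365 days at the same rate gives (425 × 14.29 + 90 × 200) / 515 = 46.7, a factor of 3.3, for 90 ITI days. For 365 ITI days it gives (425 × 14.29 + 365 × 200) / 790 = 100.1, a factor of 7.0. The factor is also per ITI subject and does not carry over to a group or overall figure.

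**Conclusion.** The point holds for the inhibitor-subgroup consumption table and for the per-patient overall value, including any overall summary made to meet Protocol 16.2.3. It does not extend to the by-regimen table or to the pre-inhibitor part of the sub-classification tables.

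For an ITI subject the inflation runs from about 1.7 to about 30 times in scenarios built on the documents' 25 to 65 IU/kg range. It depends on the assumed prophylaxis rate, the ITI share of time, and treating taper as ordinary prophylaxis. The effect on a group mean cannot be stated without the number of ITI subjects. A median over all subjects may move little.

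Pooling the whole period also departs from Protocol 16.2.1, and SAP Section 10 does not record this. The sub-classification split comes closer to that rule but cuts at the first positive sample, not at the last negative test. For a secondary, descriptive endpoint this should be corrected, but it does not threaten the trial's primary result.

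**What to change.** In SAP 6.6.1.4 and 7.4.7:
- Compute the inhibitor-subgroup and any overall annualized consumption with ITI-regimen doses and ITI-regimen days both removed.
- Report consumption during ITI separately, showing rFVIIIFc given for bleeds in that time (permitted by Protocol 10.2.7.2) by injection reason, so that it is not lost.
- Define the filter by the ITI regimen dates in SAP 5.2.3, not by the ITI period in SAP 5.4.8. The latter runs to study completion or withdrawal and would also remove taper and monitoring.
- State that taper counts as prophylactic regimen, as SAP 5.2.3 has it, or show it on its own.
- If total product use is wanted, give the ITI-inclusive value as a labelled row.
- Reconcile the inhibitor-subgroup split with Protocol 16.2.1, including the cut date, and record any departure in SAP Section 10.

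The regimen dates and injection reasons are already collected, so the cost is SAP wording, a filter and one extra row. One side effect needs a decision: the consumption denominator would no longer match the ABR denominator, which uses the same efficacy period (SAP 7.4.3), unless the ABR shown alongside is split in the same way.
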